A therapeutic trial for safety and preliminary efficacy of the combination of axitinib and selenium in the chemical composition of selenomethionine (SLM) for adult patients with advanced metastatic clear cell renal cell carcinoma (CCRCC)

Lead Institution: **University of Iowa Hospitals and Clinics
Holden Comprehensive Cancer Center**

Principal Investigator: [name]

Clinical Sub-Investigators: [name]
[name]
[name], ARNP
[name], PA-C
[name]

Laboratory Sub-Investigator: [name]
[name]
[name]
[name]
[name] Ph.D
[name]
[name]

Statistician: [name] Ph.D
[name], MS

Translation research consultant: [name] Ph.D

IND number: **126767**

Study drug: **Selenomethionine (SLM)**

Phase: **1**

Indication: **Advanced metastatic renal cell carcinoma (Stage IV)**

**Protocol Version 13.2 28Dec2022
IRB # 201507716**

SCHEMA

A Phase 1 trial for safety and preliminary efficacy of the combination of axitinib and selenomethionine (SLM) for adult patients with advanced metastatic clear cell renal cell carcinoma (CCRCC)

Escalation Part 1: COMPLETED

Dose-escalation: SLM administrated orally twice daily for 14 days, followed by once daily dosing in combination with axitinib 5 mg twice daily with titration according to package insert (listed in this protocol 5.1 Experimental Design Synopsis) in patients with advanced renal cell carcinoma. Treatment will continue until disease progression or unacceptable toxicity.

Expansion Part 2: ENROLLMENT COMPLETE

[figure not shown]
In this phase, patients will be treated at the maximum tolerated dose (MTD) of SLM determined in the Escalation Part 1 given orally twice daily for 14 days, followed by once daily dosing in combination with axitinib 5 mg twice daily with titration according to package insert (listed in this protocol 5.1 Experimental Design Synopsis) in patients with advanced renal cell carcinoma. Treatment will continue until disease progression or unacceptable toxicity.

Pilot phase: Extra 10 patients will be treated with SLM doses based on BSA as illustrated in the statistical part.

Patient population:

Advanced metastatic renal cell carcinoma (Stage IV), who have had at least one standard treatment or clinical trial including tyrosine kinase inhibitors (TKI), mammalian target of rapamycin inhibitors (mTOR-I) or immunotherapy

Experimental Design Schema showing the schedule for every patient enrolled in the study:

*The biopsy will be done only in the Expansion and Pilot in up to 20 carefully selected patients as detailed in the protocol, however the blood draw will be done on all patients.

Escalation Part 1 (Estimated number of patients: 6-12)

```
graph TD; A[Escalation Part 1] --> B[MTD determined]; B --> C[Expansion Part 2];
```

Objectives:

- Characterize the safety of combination
- Define RP2D

MTD determined

Expansion Part 2 (Estimated number of patients: 19)

Objectives:

- Biomarkers
- Preliminary efficacy

Mandatory biopsy to be done on Day 1, 14 and Cycle 3 (8 weeks after first dose of SLM plus Axitinib) in expansion part 2 and pilot Phase , before and after giving SLM.

Refer to SLM Study Lab Calendar section 20.0 for SLM concentration blood draws.

Throughout the protocol SLM dose refers to the actual elemental selenium dose that patient is getting.

— Down-regulation
→ Up-regulation

[figure not shown]

Table of Contents

1.0	OBJECTIVES	11
1.1	Primary Objectives	11
1.2	Secondary Objectives	11
2.0	BACKGROUND	12
2.1	Study disease (Renal cell carcinoma)	12
2.2	Study drug	12
2.3	Clinical Studies with Selenomethionine	13
CR (Complete response), PR (Partial response) sd (stable disease) pd (progressive disease)	14
In light of these findings, a modified dosing scheme is being investigated which varies the dosage of selenium by BSA within a dose level to ensure less variability in the dose per m ² administered	14	
2.4	Hypoxia induced factor (HIF- α):.....	14
2.5	Axitinib as a second line therapy in metastatic CCRCC.....	15
2.6	Study rationale	16
2.6.1	Rationale for Targeting HIF- α and VEGF-A Clinical Data.....	16
2.6.2	Clinical Safety of SLM using the Proposed Dose (3600 μ g/m ² equivalent to 7200 μ g, assuming patient BSA is 2.0m ²)	17
2.6.3	Preclinical Data in Support of the Rationale for the Proposed Trial.....	17
2.7	Hypothesis to be tested:.....	21
3.0	PATIENT SELECTION	23
3.1	Eligibility Criteria.....	23
3.2	Exclusion criteria	23
3.3	Inclusion of Women and Minorities.....	24
4.0	ENROLLMENT PROCEDURES	25
4.1	Enrollment Process	25
4.1.1	Consent Process	25
4.1.2	Eligibility Assessment	25
5.0	TREATMENT PLAN	27
5.1	Experimental Design Synopsis.....	27
5.2	Study Agent Administration	29
5.3	SLM and Axitinib Administration	30
5.4	General Concomitant Medication and Supportive Care Guidelines	30
5.5	Duration of Follow-up	30
5.6	Evaluations during Screening and treatment.....	31

5.7	End of treatment.....	32
5.8	Evaluable Populations.....	32

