5.0 TREATMENT PLAN

5.1 EXPERIMENTAL DESIGN SYNOPSIS

The study is designed as a prospective Phase 1 trial of SLM and axitinib in adult patients with advanced or metastatic clear cell renal cell carcinoma, who have had at least one standard treatment including tyrosine kinase inhibitors (TKI) or mammalian target of rapamycin inhibitors (mTOR-I). There must be imaging confirmation of tumor progression after completing a course of standard treatment. SLM and Axitinib will be provided through the study. The information below regarding the dose levels is not applicable to the Pilot phase.

Dose Levels for Escalation and Expansion Phases	Selenium in the chemical composition of SLM	Axitinib
-2	1500 µg administrated orally twice daily for 14 days followed by 1500 µg once daily in combination with axitinib	5 mg oral twice daily with titration according to package insert (listed in this protocol 5.1 Experimental Design Synopsis)
-1	2500 µg administrated orally twice daily for 14 days followed by 2500 µg once daily in combination with axitinib	5 mg oral twice daily with titration according to package insert (listed in this protocol 5.1 Experimental Design Synopsis)
0	3000 µg administrated orally twice daily for 14 days followed by 3000 µg once daily in combination with axitinib	5 mg oral twice daily with titration according to package insert (listed in this protocol 5.1 Experimental Design Synopsis)
1 (starting dose)	4000 µg administrated orally twice daily for 14 days followed by 4000 µg once daily in combination with axitinib	5 mg oral twice daily with titration according to package insert (listed in this protocol 5.1 Experimental Design Synopsis)

**All dose levels: starting on day 15, SLM will be taken once daily in combination with axitinib.

Escalation Part 1: COMPLETED: Last patient enrolled 10/23/2018.

Patient will start the assigned dose of SLM for 14 days and then will resume taking SLM orally at the same dose, combined with axitinib 5 mg twice daily with titration according to package insert (listed in this protocol 5.1 Experimental Design Synopsis).

Safety assessment will follow the guidelines provided in the National Cancer Institute Common Terminology Criteria for Adverse Events (NCI-CTCAE) Version 4.03.

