Patients will be followed both clinically and radiographically (CT) at baseline then every 8 weeks after starting the treatment. Responses will be assessed using RECIST 1.1 criteria. Dose level 1 (4000 µg) will be the starting dose in the standard 3+3 dose escalation design. Three patients will be recruited for Dose level 1.

The next three patients will be recruited for Dose level -1 (2500 µg). While none of the three patients in Dose level 1 experienced a DLT, there were significant side effects. If 0 of three patients at Dose level -1 experiences a DLT related to SLM, then dose escalation will proceed to the next dose level (3000 µg).

If one of the three patients at Dose level -1 experiences a DLT related to SLM, then three more patients will be treated at the same dose. If exactly one out of six patients experiences a DLT, then dose escalation will proceed to the next dose level (3000 µg) after discussion at the weekly SLM meeting.

If two of the first three patients experience DLT related to SLM, then the dose will de-escalate to the lower dose (1500 µg).

The next patient can be enrolled after the previous patient's 28th Day of SLM assessment, provided there are no DLTs related to SLM. The minimum number of patients required is 6 and the maximum is 12.

Dose Limiting Toxicities:

DLTs related to SLM will be defined as any of the following events determined by the Investigator to be related to treatment combination irrespective of outcome. This applies to the first cycle only (2 weeks SLM alone + 4 weeks combination therapy):

- Clinically significant non-hematologic toxicity of Grade 3 or greater not related to underlying malignancy.
- Severe hematological toxicity (Grade 4 neutropenia, Grade 3-4 febrile neutropenia, or Grade 4 thrombocytopenia).
- If resolution of DLT related to SLM does not occur in 4 weeks, then patient will be withdrawn from the study.
- Grade 4 nausea, vomiting, diarrhea, or electrolyte imbalances or Grade 3 nausea, vomiting, diarrhea and electrolyte imbalances lasting greater than 48 hours despite optimal medical intervention.
- In the dose escalation phase, treatment delays related to the study drug that last >2 weeks

- Any grade 3 or higher DLT related to SLM alone will be discussed at the weekly SLM committee meeting.
-

Expansion Part 2: Enrollment Completed

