After completing the Escalation Part 1 and based on the safety results, we will initiate an expanded cohort, Expansion Part 2 including a total of 19 patients with advanced metastatic CCRCC, to be treated with SLM 4000 in combination with axitinib 5 mg PO BID.

Up to 20 patients in the Expansion Part 2 and pilot phase will have mandatory biopsies at baseline before the start of SLM that will be repeated around day 14 (+/- 3 days) after starting SLM, at Cycle 3 (8 weeks +/- 3 days after first dose of SLM plus Axitinib) and preferably at disease progression, preferably from the same site of the previous biopsy, to study the expression of HIF-a and VEGF by immunohistochemistry (IHC), along with other biomarkers detailed in the correlative studies, before and after treatment with SLM. These tissues will be flash frozen and stored at -80 C to be processed later all at once for the proposed biomarkers.

The candidate patients for the biopsies will be chosen carefully by the treating oncologist and after discussion with the interventional/ body radiologist. Decision will be based on safety, ease of accessibility, tumor size and feasibility of getting the biopsy which can be done either on the primary renal tumor or metastatic site. Patient has to agree to get the biopsies, and sign consent form, after discussing the risks and benefits of the procedure with the provider.

All patients will have a peripheral blood draw at baseline before the start of SLM and repeated on day 14 after starting treatment. This blood will be stored and may be used later to study the protein expression of HIF1a, HIF2a, VEGF and level of SLM.

For Escalation Subjects: All patients will have a peripheral blood draw at baseline before the start of SLM and repeated on day 14 after starting treatment.

For Expansion Subjects: the peripheral blood draw will occur pre-dose and 2 hours post dosing on day 1 then 2 hours post dosing on Day 14 and at Cycles 2, 3, 4, 7, 10 and 13.

Pilot Phase: BSA based dosing. See additional details in protocol Section 14.4.

5.2

STUDY AGENT ADMINISTRATION

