14.0 STATISTICAL CONSIDERATIONS

14.1 INTRODUCTION

This is a Phase I safety clinical trial with expansion cohort for assessing preliminary efficacy of the combination of axitinib and selenomethionine (SLM) for adult patients with advanced clear cell carcinoma (CCRCC). The Escalation Part 1 will determine the MTD of the combined treatment to be used for the proof of principle. The expansion cohort will be used to assess preliminary efficacy.

Summary statistics for continuous variables will include: mean, standard deviation, median and range. Categorical variables will be presented as frequency counts and percentages. Progression-free and overall survival will be summarized by Kaplan-Meier medians and survival plots. Data listings will be created to support tables and present data. The preliminary efficacy analysis will be conducted on the efficacy evaluable population and safety analysis will be performed on the safety population. SAS 9.3 or higher will be used for data analysis.

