14.3 ANALYSIS OF STUDY ENDPOINTS

14.3.1 Analysis of primary endpoint

a. The safety profile of the SLM and axitinib combination will be assessed by listing the overall incidence of AEs. The AEs will be summarized and classified by body system and by treatment group. The type, incidence, severity, and causality of each AE, the duration of the event, and any required treatment interventions will be tabulated. Physical examination results will be presented in the patient data listings. The DLT will be listed per dose level and treatment along with overall frequencies. The data from the expansion part will be used for this part of safety and tolerability assessment.

b. (Recommended Part 2 dose)

Dose level 1 (4000 µg) will be the starting dose in the standard 3+3 dose escalation design. Three patients will be recruited for Dose level 1.

The next three patients will be recruited for Dose level -1 (2500 µg). While none of the three patients in Dose level 1 experienced a DLT, there were significant side effects.

If 0 of three patients at Dose level -1 experiences a DLT related to SLM, then dose escalation will proceed to the next dose level (3000 µg).

If one of the three patients at Dose level -1 experiences a DLT related to SLM, then three more patients will be treated at the same dose. If exactly one out of six patients experiences a DLT, then dose escalation will proceed to the next dose (3000 µg) after discussion at the weekly SLM meeting.

If two of the first three patients experience DLT, then the dose will de-escalate to the lower dose (1500 µg).

The next patient can be enrolled after the previous patient's Day 28 assessment, provided there are no DLTs. The minimum number of patients required is 6 and the maximum is 12.

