Dose escalation for this pilot study will be conducted using a continual reassessment method (CRM) in which the probability of exceeding a blood selenium concentration of 45 μM on Day 14 is being modeled. Prior probabilities of exceeding a blood selenium concentration of 45 μM on Day 14 were estimated based on preclinical and preliminary data from the initial trial. A one parameter logistic model with intercept set at 3 and an initial value of 1 for the slope will be used to estimate the dose-concentration relationship through sequential recursive Bayesian assessment. The target probability of exceeding 45 μM is $\leq 20\%$.

BSA	Dose Level ^a				
	1	2	3 ^b	4	5
1.50-1.79	2000	3000	4000	5000	6000
1.80-2.19	3000	4000	5000	6000	7000
2.20-2.49	4000	5000	6000	7000	8000
π_{45}^c	0.001	0.01	0.10	0.20	0.30

^aAll doses are mcg BID Day 1-14 then daily until progression.

^bStarting dose level.

^cProbability of exceeding 45 μM (prior)

[figure not shown]
Dosing will begin at dose level 3. Each cohort will enroll 2 evaluable patients. After each patient has completed the Day 14 evaluation, the following information will be provided to the statistical research team:

1. Blood selenium concentration on Day 14
2. DLTs, defined as any of the following treatment-related events occurring between Day 1 and 14 irrespective of outcome:
 - a. Clinically significant non-hematologic toxicity of Grade 3 or greater not related to underlying malignancy.
 - b. Severe hematological toxicity (Grade 4 neutropenia, Grade 3-4 febrile neutropenia, or Grade 4 thrombocytopenia).
 - c. Grade 4 nausea, vomiting, diarrhea, or electrolyte imbalances or Grade 3 nausea, vomiting, diarrhea and electrolyte imbalances lasting greater than 48 hours despite optimal medical intervention.

At which time, the dose-concentration model will be updated to obtain the recommended dose level for the subsequent cohort. Dose escalation will proceed one dose level at a time; skipping dose levels is not permitted.

Simulations

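### The plan calls the 4000 mcg expansion dose the MTD, but the Part 1 escalation as written and reported does not support that label, and the pilot dose table conflicts with it

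*Combined protocol and SAP*

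**What the plan says.** **The label.** The Schema states that in the expansion "patients will be treated at the maximum tolerated dose (MTD) of SLM determined in the Escalation Part 1", and its flow chart places an MTD-determined step between the two parts. Section 14.1 says: "The Escalation Part 1 will determine the MTD of the combined treatment to be used for the proof of principle".

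**The dose.** Section 5.1 describes the 19 expansion patients as "to be treated with SLM 4000 in combination with axitinib 5 mg PO BID".

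**The ladder.** The section 5.1 table has four levels: -2 (1500 mcg), -1 (2500 mcg), 0 (3000 mcg) and 1 (4000 mcg). Level 1 "will be the starting dose in the standard 3+3 dose escalation design". There is no row above it.

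**What happened at 4000 mcg.** Sections 5.1 and 14.3.1(b) both report: "While none of the three patients in Dose level 1 experienced a DLT, there were significant side effects". The next cohort went to 2500 mcg. From there the rules lead up to 3000 mcg or down to 1500 mcg.

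**A second 4000 mcg cohort.** Section 2.3 lists four cohorts: C1 at 4000, C2 at 2500, C3 at 3000 and C4 at 4000 mcg. It gives selenium levels and tumour responses for each (three responses for C4), but no DLT counts.

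**The pilot.** Section 14.4 says "Dosing will begin at dose level 3". Level 3 is 4000, 5000 or 6000 mcg twice daily for BSA 1.50-1.79, 1.80-2.19 and 2.20-2.49. The table goes up to 8000 mcg.

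**The concern.** To most readers, MTD means that higher dosing was found, or can be inferred, to be too toxic. A 3+3 design shows this by testing a level above the declared dose and finding too many DLTs there. Part 1 had no level above 4000 mcg, and the step down to 2500 mcg was prompted by side effects that the protocol says were not DLTs. The documents give no criterion that would turn such side effects into an MTD decision, and 4000 mcg was later used for the expansion anyway.

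Defining the SLM dose for the expansion and for a later phase 2 trial is a primary objective (sections 1.1 and 14.2). If 4000 mcg is carried forward as an MTD, later readers will assume an upper bound that the documented escalation does not show. They will also see a pilot that, by the protocol's own label, opens above the MTD for some patients, with nothing to reconcile the two statements.

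**Working it through.** The plan gives no calculated figure to reproduce. The check sets the ladder, the reported count and the pilot table side by side.

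**1. Can the written rules yield an MTD of 4000 mcg?** The ladder is 1500 < 2500 < 3000 < 4000, starting at 4000. After level 1 the text goes to 2500, then to 3000 (0 of 3, or exactly 1 of 6, with a DLT) or to 1500 (2 of the first 3). No rule covers a return from 3000 to 4000, a step above 4000, or how the MTD is declared. C4 shows that a return took place, if C4 belongs to Part 1. Section 2.3 does not say so, but the order of the doses fits, and the listed responses total 3 + 2 + 3 + 3 = 11, within the Part 1 maximum of 12.

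**2. What does 0 of 3 show?** The exact one-sided 95% upper limit with no events in n patients is 1 - 0.05^(1/n).
- n = 3: 1 - 0.05^(1/3) = 63.2% (two-sided 95% interval: upper limit 70.8%).
- The chance of 0 of 3 at a true DLT rate p is (1 - p)^3: 51.2% at p = 20%, 29.6% at p = 1/3 and 12.5% at p = 50%.

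**3. Could C4 rescue the label?** Its DLT count is not given. Assuming three evaluable patients in each 4000 mcg cohort:

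| DLTs at 4000 mcg | One-sided 95% upper limit | Two-sided 95% upper limit | Reading under a conventional 3+3 |
|---|---|---|---|
| 0 of 6 | 1 - 0.05^(1/6) = 39.3% | 45.9% | Acceptable, but no higher level was tested |
| 1 of 6 | 58.2% | 64.1% | Acceptable, but no higher level was tested |
| 2 or more of 6 | not computed | not computed | 4000 mcg would lie above the MTD |

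The limits for 1 of 6 are Clopper-Pearson. With 0 or 1 DLT, 4000 mcg is only the highest level tested. With 2 or more, it is not the MTD. No row makes 4000 mcg an MTD bounded by a more toxic level.

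**4. Pilot starting doses against 4000 mcg.** The schedule is the same as in the expansion (twice daily for 14 days, then once daily), so the flat doses compare directly.
- BSA 1.50-1.79: 4000/4000 = 1.00
- BSA 1.80-2.19: 5000/4000 = 1.25
- BSA 2.20-2.49: 6000/4000 = 1.50

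Per m², level 3 runs from 4000/1.79 = 2235 to 5000/1.80 = 2778 mcg/m². A flat 4000 mcg at BSA 1.50 is 4000/1.50 = 2667 mcg/m². At BSA 2.0, the reference value in section 2.6, level 3 gives 5000/2.0 = 2500 mcg/m² against 4000/2.0 = 2000 mcg/m² in the expansion.

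**The case against.** **The objective is a recommended dose, not an MTD.** This is correct. Sections 1.1 and 14.2 ask for the dose for the expansion and phase 2, and section 14.3.1(b) is headed as the recommended Part 2 dose. Such a dose can be chosen without an MTD. It would therefore be wrong to infer that the primary objective fails. The point concerns the label.

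**MTD may be meant loosely, as the highest dose given with few DLTs.** Section 9.1 uses the term that way for the earlier irinotecan combination study, while saying that the non-tolerable dose was not defined there. But this protocol does not adopt that meaning, and even the loose meaning needs the C4 count.

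**The higher pilot doses are addressed openly.** Section 14.4 explains the BSA rationale, cites experience up to 7200 mcg with a shorter run-in, and pauses accrual for DSMC review after any run-in DLT. Per m², the level 3 maximum is only about 4% above what a flat 4000 mcg gives at BSA 1.50 (2778/2667 = 1.04). All of this stands, so the pilot table is no evidence of an unsafe design. It still does not explain how those doses sit beside a declared MTD of 4000 mcg.

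**More data at 4000 mcg will exist.** Section 14.3.1(a) already plans DLT listings per level and uses the expansion data for tolerability, so the 63% limit is not the final evidence on this dose. But more patients at 4000 mcg do not test a higher level, and the text credits Part 1 with the MTD.

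**Two stronger readings are tempting and not supported.** A reader might infer that the MTD was not reached. That cannot be said without the C4 DLT count, since 2 or more DLTs in 6 would contradict it. A reader might also infer that the pilot starts most patients above 4000 mcg. The documents give no BSA distribution. Assuming a normal BSA with mean 1.75 to 2.05 and SD 0.15 to 0.25 m², the share at 1.80 or more ranges from 37% to 95%. Only the statement about patients with BSA of 1.80 or more is documented.

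**Conclusion.** The concern holds for the label. As written and reported, Part 1 does not support calling 4000 mcg an MTD: it is the start and the top of the ladder, its one reported count of 0 of 3 is compatible with a DLT rate of up to 63% (one-sided 95%), no declaration rule exists, and the return to 4000 mcg is undocumented. Whatever C4 showed, the data cannot bracket an MTD at 4000 mcg. This last step assumes three evaluable patients in each 4000 mcg cohort and the usual 3+3 reading of at most 1 DLT in 6. If C4 was not part of Part 1, the Part 1 evidence stays at 0 of 3.

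The conflict with the pilot table is one of wording: two of the three BSA bands start 25% and 50% above the declared MTD, and the lowest band starts exactly at it. Nothing here says that 4000 mcg or any pilot dose is wrong.

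**What to change.** 1. Reconcile the Schema, section 5.1 (dose table, escalation rules and expansion dose), section 14.1, section 14.3.1(b) and the pilot table in section 14.4.
2. Report DLTs for each Part 1 level, with C1 and C4 shown separately and combined, using the DLT-evaluable population of section 5.8 as denominator and exact confidence limits. Section 14.3.1(a) already plans the listing, so the additions are the limits and an explicit C4 count. Record on what basis dosing returned to 4000 mcg.
3. Then do one of two things. Either state the rule by which an MTD was declared and show that the counts meet it, or drop the MTD claim and describe 4000 mcg as the dose selected for expansion and the highest level tested in Part 1.
4. Say in section 14.4 how that statement relates to pilot doses above 4000 mcg.

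The cost is wording and one tabulation of data already collected. The downside is a less favourable description of Part 1. Which dose is right is not for this review to decide.
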